4.4 SECONDARY OUTCOME MEASURES

4.4.1 Safety

Safety will be evaluated by any of the following adverse events that occur over the duration of the study:

- 1. Any death
- 2. All serious adverse events (SAE) regardless of relation to the device or procedure
- 3. Any non-serious adverse event (AE) that is classified as either device or procedure-related
- 4. Any unanticipated adverse device effect (UADE)

Adverse events will be summarized by relation to the study devices or study procedure. Overall occurrence rate by event type will also be calculated.

4.4.2 Procedure Parameters

The following procedural parameters will be recorded on all subjects:

- 1. Device implant time: Mean (\pm SD) implant time defined as follows:
 - Open procedure: Time from introduction of the bioinductive implant into the surgical field to completion of the last staple
- 2. Procedure technical success: The proportion of subjects where the device was successfully delivered and affixed to target tendon location.
- 3. Device implant position: An intra-operative photograph(s) or video recording showing the implant location of the device and all tendon and bone staples will be obtained.

4.4.3 Recovery

The following post-operative recovery parameters will be reported after discharge from the from study procedure:

- 1. CAM boot time: cumulative number of days spent in a CAM boot
- 2. Rehabilitation time: cumulative number of completed rehabilitation or physical therapy (PT) visits (mean \pm SD) to treat index Achilles
- 3. Return to work: cumulative number of days (mean \pm SD) between discharge and return to work (employed subjects only)
- 4. Return to normal daily activities (i.e. full, unrestricted activity): cumulative number of days (mean \pm SD) between discharge and return to normal daily activity

4.4.4 Subject Satisfaction

Subject satisfaction is a self-reported measure of satisfaction with the outcome of the index surgery. The level of satisfaction is assessed with a 5-point Likert scale. Each subject will also be asked to indicate whether (s)he would recommend the study procedure to a friend ("yes/no").

5 STATISTICAL ANALYSIS PLAN

This is an initial feasibility study and not powered to address the hypotheses. Changes in tendon thickness over the time of the follow up visits will be assessed by a Repeated Measures ONEWAY ANOVA with a post hoc Scheffe. Indices of new tissue integration and maturation at each follow up visit will be assessed by Chi Square analyses.

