Study Objective:	To evaluate bioinduction of new tissue and tendon healing after implantation of the Rotation Medical Bioinductive Implant used as adjunct to surgical repair in the treatment of insertional Achilles tendonitis.				

MRI assessment of the following:			
1. Increase in tendon thickness			
2. Integration of induced tissue with the underlying tendon and maturation of			
the induced tissue			
3. Amount of defect fill-in and characteristics of both the filled-in tissue within			
the tendon			
4. Achilles tendon tear rate at surgical site			
1. Safety			
2. Procedure parameters			
3. Recovery			
4. Subject satisfaction			
Baseline			
Procedure			
Post-procedure follow-up: 3 months, 1 year, 2 years			
Rotation Medical, Inc.			
[name]			
[name]			
Datation Madical Inc			
Rotation Medical, Inc.			
[name]			
[name]			

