4.3 PRIMARY OUTCOME MEASURES

4.3.1 Increase in Tendon Thickness

Achilles tendon thickness will be measured pre-operatively (baseline) and the total thickness of the tendon and any newly induced tissue at the implant site will be measured at each follow-up visit using magnetic resonance imaging (MRI). The mean (\pm SD) change in post-operative Achilles tendon thickness will be calculated at each follow-up interval.

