7 STUDY ASSESSEMENTS

The schedule of protocol-required study assessments is provided in **Table 7.1**. Adverse event (AE) reporting as required and defined in **Section 8** begins at the time of enrollment (i.e. intra-operative confirmation of eligibility) and concludes at the end of the study.

Table 7-1: Schedule of Study Assessments

	Baseline	Procedure	3-Month	1 Year	2 Year
Study Evaluation	Within 60 Days of Surgery	Within 60 Days of Baseline	± 15 days	± 45 days	± 90 days
Informed Consent	✓				
Medical History & Exam	✓				
Eligibility Assessment	✓	√ ¹			
Enrollment (Date of Surgery)		✓			
MRI	√ ²		✓2	✓2	√ ²
Procedure Data		✓			
Medications	✓3	✓3	✓3	✓3	✓3
Adverse Events		✓4	✓4	✓4	✓4
Recovery/Satisfaction			✓	✓	✓
Questionnaire					
Revision/Additional Achilles Surgery			√ 5	√ 5	√ 5

¹Eligibilty confirmation will be performed at the time of the study surgery to ensure the patient meets eligibility criteria. Patients who do not meet study eligibility criteria will not be enrolled in the study.

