7.6 POST-OPERATIVE CARE

Post-operative care, including discharge instructions, pain management, and frequency/duration of physical therapy/rehabilitation regimen are at the discretion of the surgeon. To minimize the likelihood that the integrity or position of the device is compromised after implant, recommended rehabilitation guidelines are provided in **Table 7.2.**

Table 7-2: Post-operative Rehabilitation Guidelines

Study Procedure	Rehabilitation Guidelines			
Device implant	Remain in post mold splint until follow up			
	Remain nonweight bearing on operative leg with crutches or walker			
	• Follow up in one week for evaluation and placement into CAM boot with heel lift			
	• Follow up at 2 weeks for suture removal			
	• Follow up at 4 weeks for partial heel lift removal and progression to neutral foot			
	Follow up at 4 weeks for start of physical therapy			
	• Fill out VISA-A (Victorian Institute of Sports Assessment-Achilles questionnaire) at 6 and 12 months			

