7.7 FOLLOW-UP ASSESSMENTS

All subjects will undergo post-operative study assessments at 3 months, 1 year, and 2 years after discharge from the study procedure as described below and summarized in **Table 7.1**.

7.7.1 3-Month (± 15 Days) Follow-Up

- 1. Perform an MRI per the Sponsor Imaging guidelines.
 - Provide the Sponsor with a de-identified digital copy of, or access to, the MRI
- 2. Clinical Assessment
- 3. Record prescription medications
 - Record any prescription medications the subject is taking at the time of the follow-up visit to treat his/her index Achilles.
- 4. Record any new adverse events and update the status of any ongoing, previously-reported adverse events.
- 5. Report any new revision/additional Achilles surgeries performed on the index Achilles

7.7.2 1-Year (\pm 45 Days) Follow-Up

- 1. Perform an MRI per the Sponsor imaging guidelines.
 - Provide the Sponsor with a de-identified digital copy of, or access to, the MRI.
- 2. Clinical assessment
- 3. Administer the recovery/satisfaction questionnaire (VISA-A)
- 4. Record prescription medications.
 - Record any prescription medications the subject is taking at the time of the follow-up visit to treat his/her index Achilles.
- 5. Record any new adverse events and update the status of any ongoing, previously-reported adverse events.
- 6. Report any new revision/additional Achilles surgeries performed on the index Achilles.

7.7.3 2-Year (\pm 90 Days) Follow-Up

1. Perform an MRI per the Sponsor imaging guidelines.

- Provide the Sponsor with a de-identified digital copy of, or access to, the MRI.
- 2. Clinical assessment
- 3. Administer the recovery/satisfaction questionnaire.
- 4. Record prescription medications.
 - Record any prescription medications the subject is taking at the time of the follow-up visit to treat his/her index Achilles.
- 5. Record any new adverse events and update the status of any ongoing, previously-reported adverse events.
- 6. Report any new revision/additional Achilles surgeries performed on the index Achilles.

The results of all follow-up assessments will be documented on their respective CRFs. Each reportable adverse event (**Section 4.1.1**) will be documented on an Adverse Event CRF.

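### Section 5 does not name the pre-operative MRI as a level of the thickness ANOVA; read literally, the test compares the three follow-up visits with each other and does not test the increase from baseline

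*Combined protocol and SAP*

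**What the plan says.** Section 4.3.1 makes an increase in Achilles tendon thickness a primary outcome. Thickness is measured by MRI before surgery and at every follow-up visit, and the mean (SD) "change in post-operative Achilles tendon thickness will be calculated at each follow-up interval". No test is attached to that summary.

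The inferential test appears only in Section 5: "Changes in tendon thickness over the time of the follow up visits will be assessed by a Repeated Measures ONEWAY ANOVA", followed by a post hoc Scheffé procedure. Section 5 gives no levels for the time factor, no reference visit for the Scheffé comparisons and no test of the mean change against zero. It opens with the statement "This is an initial feasibility study and not powered to address the hypotheses".

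Wherever study MRIs are scheduled, baseline and follow-up are kept apart:

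- The synopsis lists baseline, then the procedure, then "Post-procedure follow-up: 3 months, 1 year, 2 years".
- Table 7-1 has a separate baseline column, timed "Within 60 Days of Surgery".
- Section 7.7 states: "All subjects will undergo post-operative study assessments at 3 months, 1 year, and 2 years after discharge from the study procedure".

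Section 7.6 uses the term more loosely for early care visits, for example "Follow up in one week for evaluation and placement into CAM boot with heel lift", but no MRI is scheduled at those visits.

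**The concern.** The outcome is an increase, so it needs a comparison with the pre-operative value. A repeated-measures ANOVA restricted to the follow-up visits makes a different comparison, namely whether thickness at 3 months, 1 year and 2 years is the same. A gain that is fully present at 3 months and then holds would leave nothing for that test to find. A significant result would show only that the visits differ, which is also what a gain followed by a loss would produce.

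Two things are at stake. On the literal reading, the only named test for this primary outcome does not address it. And because the levels are not stated, the choice between three and four levels could be made after the data are seen.

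**Working it through.** The documents give no power or sample-size calculation, so there is no plan figure to reproduce.

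**Inputs from the documents.** Up to 10 subjects in a single arm (Section 4.1); one pre-operative and three follow-up MRIs (Table 7-1); one-way repeated-measures ANOVA with Scheffé (Section 5).

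**Assumptions.** Complete data, normality, two-sided 5% level, equal variance at each visit, and gain in units of the SD of thickness at one visit. Four correlation settings (baseline with follow-up / between follow-ups) were tried: 0.5/0.5, 0.3/0.7, 0.4/0.8 and 0.2/0.8. The documents supply none of these values.

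**Step 1: change scores do not alter the test.** Let Y_ij be the thickness of subject i at follow-up j, B_i the baseline, and D_ij = Y_ij − B_i. The F-ratio uses two quantities:

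- Time effect: D_.j − D_.. = (Y_.j − B_.) − (Y_.. − B_.) = Y_.j − Y_..
- Residual: D_ij − D_i. − D_.j + D_.. = Y_ij − Y_i. − Y_.j + Y_..

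Baseline cancels from both, so F is identical. Numerically, the largest difference over 500 simulated data sets was about 4 × 10⁻¹⁴.

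**Step 2: constant gain δ, n = 10.**

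- Three levels (df 2, 18): the means are δ, δ, δ, the sum of squared deviations is 0, the noncentrality is 0, and the rejection rate is the 5% type I error for any δ.
- Four levels (df 3, 27): the means are 0, δ, δ, δ, with grand mean 0.75δ. The sum of squares is (0.75² + 3 × 0.25²)δ² = 0.75δ². With δ = 1 and all correlations 0.5, the noncentrality is 10 × 0.75 / (1 − 0.5) = 15, and power is 87%.

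**Step 3: simulation over the four settings (40,000 trials each).**

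| Setting | 3 levels, constant gain | 4 levels, 1 SD gain | Same, Greenhouse-Geisser | 4 levels, no gain | Same, Greenhouse-Geisser |
|---|---|---|---|---|---|
| 0.5/0.5 | 5% | 87% | 82% | 5.1% | 3.4% |
| 0.3/0.7 | 5% | 79% | 71% | 6.5% | 4.2% |
| 0.4/0.8 | 5% | 86% | 78% | 7.0% | 4.4% |
| 0.2/0.8 | 5% | 75% | 64–65% | 7.9% | 4.8% |

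The three-level column holds for gains of 0.5, 1, 2 and 3 SD. The no-gain columns show why a sphericity correction is needed once baseline is a level. Section 7.5 puts detachment, debridement and re-attachment between baseline and every follow-up, so equal correlation is doubtful.

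**Step 4: gain still rising.** The three-level test then has power: 14–28% for 0.7/1/1 SD at the three visits, 31–66% for 0.5/1/1, and 40–79% for 0.33/0.67/1. For 0.5/1/1 the sum of squares is 0.1667. The noncentrality is 10 × 0.1667 / 0.5 = 3.33 at between-follow-up correlation 0.5 (31%) and 10 × 0.1667 / 0.2 = 8.33 at 0.8 (66%). The test responds to differences between visits, not to the gain.

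**Step 5: follow-up against baseline, 1 SD gain.** The Scheffé multiplier is √(3 × F(.95; 3, 27)) = 2.98. Scheffé contrasts in the four-level model detect the gain at a given visit in 57–68% of trials, with joint coverage of 98.4, 95.9, 95.4 and 94.6% across the settings. Bonferroni paired intervals (multiplier 2.93 at 9 df) detect it in 39–61%. Unadjusted paired intervals cover about 95% at each visit but only 87–91% jointly. Their half-width, t(.975; m−1)/√m in SDs of the paired difference, is 0.72, 0.77, 0.84 and 0.92 for 10, 9, 8 and 7 pairs.

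**The case against.** The strongest reply is that the context points to baseline. Section 4.3.1 defines the outcome as a pre-operative measurement followed by post-operative ones. Changes in Section 5 can naturally refer to that, with the phrase about follow-up visits describing the period covered, not the factor levels. This stands as a possible reading, so a reader should not infer that baseline will be left out. The documents show an unstated level, not a decision to omit it. Reading the phrase as change scores at three visits does not help, because of the cancellation in step 1.

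The second reply is that the baseline-referenced result is already promised. The mean (SD) change in Section 4.3.1, with the number of subjects, gives a paired interval by arithmetic. That stands, so it would be wrong to say that the increase goes unreported. On the literal reading it is described but not tested.

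Third, a reader might infer from Section 1 that the test is bound to fail, because thickness in sheep rose by about 2.5 mm and was stable at one year. The documents do not support that. They do not say when the gain was reached. Section 2.1 has the implant absorbing over six to 12 months, so thickness could move between the 3-month and 1-year MRIs. The sheep result is an example of a pattern that the literal test could miss, not a forecast.

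**Conclusion.** The point holds as an ambiguity with a definite consequence on one of its two readings. Taken literally, the thickness ANOVA has about a 5% chance of rejecting for a gain of any size that is equal at all three follow-ups. That part is algebra and, given the usual ANOVA assumptions, does not depend on the assumed effect sizes. The contrast with 75–87% power for four levels (about 64–82% corrected) does depend on 10 complete subjects, a gain of 1 SD and the assumed correlations.

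The impact is minor. The study is declared an unpowered feasibility study, has no control arm or success criterion, and reports the mean (SD) change in any case. Thickness is also one of several primary MRI outcomes. Nothing here shows that the sample size is wrong or that ANOVA is the wrong method. A comparison among follow-up visits remains a reasonable supplementary question about stability. The wording should still be corrected, because the two readings answer different questions and settling it costs almost nothing.

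**What to change.** State the following in Section 5 before the data are seen:

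- The levels of the thickness ANOVA are baseline (pre-operative MRI), 3 months, 1 year and 2 years, with a Greenhouse-Geisser correction to the F-test.
- The post hoc Scheffé contrasts of interest are each follow-up visit against baseline.
- The mean paired change from baseline at each visit is reported with its SD, an unadjusted t-based 95% confidence interval and the number of pairs. The intervals are labelled as per-visit and not as support for a joint statement about all three visits.

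Replacing the ANOVA and Scheffé with Bonferroni paired intervals is not needed: Scheffé detects the gain more often in three of the four settings (step 5). Making the ANOVA or the adjustment optional would reopen the choice after the data are seen.

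The cost is SAP wording only; no new data are needed. There are three downsides. The Greenhouse-Geisser correction loses about 5–11 percentage points of power in the assumed settings. Scheffé joint coverage can fall slightly below 95% (94.6% in the most unequal setting tried). Intervals from available pairs may rest on different subjects at different visits, and they do not remove bias if a missed MRI is related to thickness.

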4.1 SAMPLE SIZE

Up to 10 subjects will be enrolled and treated with the Rotation Medical Bioinductive Impant at Union Memorial hospital and the associated Surgery Center.

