6 ELIGIBILITY CRITERIA

Subjects who meet all inclusion criteria (Section 6.1) and none of the exclusion criteria (Section 6.2) will be eligible to participate in the study.

Enrollment in the study occurs upon intra-operative confirmation that the subject meets all of the inclusion criteria and none of the exclusion criteria. Subjects who meet eligibility criteria and are enrolled will be followed per protocol through the end of the study (i.e., intent-to-treat). Subjects who do not meet the study eligibility criteria at the time of surgery will not be enrolled.

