7.10 EARLY WITHDRAWAL OR LOST TO FOLLOW-UP

If a subject wishes to withdraw from the study at any time, (s)he is able to do so voluntarily without having to justify it and without affecting her/his relationship with the Investigator.

Also, an Investigator may withdraw a subject from the study at any time if (s)he thinks it is in the subject's best interest.

The subject's future management will not be changed by a decision, voluntary or otherwise, to withdraw from the study.

All reasonable efforts should be made to retain the subject in this clinical study until completion of the clinical assessments at each follow-up visit. A subject will be considered "lost to follow-up" after a minimum of 2 documented phone calls to the subject were completed by a member of the study staff and a certified letter was sent to the last known address by a traceable method (e.g., certified mail; courier; commercial shipping/transport company).

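### If any follow-up MRI is missing, the only planned thickness test would, in its standard form, drop all of that subject's scans; a mixed model would keep them

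*Combined protocol and SAP*

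**What the plan says.** Tendon thickness is the first-listed primary outcome. Section 5 is the whole statistical plan, and it gives this outcome one sentence, under which change between visits "will be assessed by a Repeated Measures ONEWAY ANOVA with a post hoc Scheffe". It names no analysis set, missing-data rule, imputation, mixed model or sensitivity analysis, and no other section supplies one. The same section says: "This is an initial feasibility study and not powered to address the hypotheses".

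Section 4.3.1 gives a descriptive summary, the mean (with SD) "change in post-operative Achilles tendon thickness will be calculated at each follow-up interval". It does not say which subjects enter it.

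Section 4.1 sets the size: "Up to 10 subjects will be enrolled and treated with the Rotation Medical Bioinductive Impant". Section 7.7 and Table 7-1 schedule MRI at 3 months, 1 year and 2 years, after a baseline MRI that Section 6.1 (criterion 4) makes a condition of entry. Section 6 says that enrolled subjects "will be followed per protocol through the end of the study (i.e., intent-to-treat", the last term standing in brackets as a gloss on follow-up. Section 7.10 provides for the case "If a subject wishes to withdraw from the study at any time" and also lets the investigator withdraw a subject. Section 7.11 exits subjects on withdrawal or loss to follow-up, so no later scan is planned for them.

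**The concern.** A classical one-way repeated-measures ANOVA is computed on a complete subject-by-visit table. Section 5 names that method and is silent on incomplete subjects, so the default is to remove any subject with a gap. Someone scanned at baseline, 3 months and 1 year who leaves before year 2 would lose three valid scans from the test.

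Two things are at stake. The first is precision: with at most 10 subjects, each one removed is 10% of the sample. The second is representativeness: if the chance of leaving is related to how the tendon is doing, the subjects left in the test differ from those treated. In addition, the per-visit means in Section 4.3.1 and the test in Section 5 could rest on different subjects, with no rule to explain the difference.

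**Working it through.** The plan has no figure of its own to reproduce: it states no alpha, power, effect size, SD or dropout rate. The miss rates below are assumptions, shown as a range.

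**Inputs from the documents.** n = 10 (Section 4.1, the maximum). There are 3 follow-up MRIs per subject (Section 7.7). Baseline MRI is always present (Section 6.1), so a full data set has 10 × 4 = 40 scans.

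**Step 1: how the method behaves.** Ten simulated subjects with four visits each were given to a standard repeated-measures ANOVA routine. With all 40 scans it ran with 3 and 27 degrees of freedom. With one scan removed it rejected the data as unbalanced. It ran again only after the whole subject was deleted, on 9 subjects and 36 scans with 3 and 24 degrees of freedom. A random-intercept mixed model on the same incomplete data used all 10 subjects and 39 scans.

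**Step 2: completers and discarded scans.** Let m be the probability that a follow-up MRI is missed, independently across visits.

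- Expected completers = 10 × (1 − m)³
- Follow-up scans obtained = 30 × (1 − m)
- Follow-up scans used by the ANOVA = 3 × completers
- Probability that at least one subject is dropped = 1 − (1 − m)³⁰

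| m | Completers | Obtained | Used | Discarded | P(at least one dropped) |
|---|---|---|---|---|---|
| 5% | 8.57 | 28.5 | 25.7 | 2.8 (9.8%) | 79% |
| 10% | 7.29 | 27.0 | 21.9 | 5.1 (19.0%) | 96% |
| 15% | 6.14 | 25.5 | 18.4 | 7.1 (27.8%) | 99% |

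Independence is not essential. If 2 of 10 subjects leave between year 1 and year 2, the scans obtained are 8 × 3 + 2 × 2 = 28. The test discards 4 of them (4/28 = 14%).

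**Step 3: precision.** With k visits in the model, the Scheffe half-width for a pairwise difference, in residual SDs, is √((k − 1) × F) × √(2/n), where F is the critical value at an assumed alpha of 0.05. For k = 4:

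- n = 10: √(3 × 2.96) × √(2/10) = 1.33
- n = 7: √(3 × 3.16) × √(2/7) = 1.65

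If baseline is not a level of the factor (k = 3), the values are 1.19 and 1.49.

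**Step 4: representativeness.** A simulation used a true change of 1.0 SD at every follow-up visit and dropout after 3 months that depended on the 3-month change (about 23% lost).

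| Who tends to leave | Completers' 3-month change | Completers' 2-year change |
|---|---|---|
| Low-change subjects | 1.36 | 1.18 |
| High-change subjects | 0.64 | 0.81 |
| Unrelated to outcome | 1.00 | 1.01 |

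Using every subject's 3-month scan gave 1.00 and 0.99 in the first two rows. Bias therefore needs outcome-related dropout; the loss of data in Step 2 does not.

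**The case against.** The strongest reply is that Section 5 never says incomplete subjects are excluded, that nobody is lost if all 40 scans are obtained, and that this is an unpowered single-arm feasibility study with no decision rule, where the descriptive means arguably matter more than the test. The protocol also tries to limit missed visits, through willingness to attend (Section 6.1, criterion 6), exclusion for past non-compliance (Section 6.2, criterion 14) and retention efforts (Section 7.10). All of this stands and limits the point. It does not remove it: the plan still specifies a test with post hoc comparisons, retention efforts are not an analysis rule, and one missed scan is enough to trigger the problem.

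Three stronger readings are tempting and are not supported.

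- A reader might infer that the ANOVA contradicts a declared intent-to-treat analysis. Section 6 uses the term for follow-up, and no analysis set is defined anywhere.
- A reader might infer that differences between visits in the test would reflect a changing cohort. They would not, because a completers-only ANOVA uses the same subjects at every visit. Changing composition can affect only the per-visit means in Section 4.3.1.
- A reader might infer that re-operated subjects drop out. Revision surgery is not a listed reason for exit. Sections 7.7 and 7.9 record it during continuing follow-up, and Section 7.2 follows every enrolled subject unless consent is withdrawn.

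The 10%, 19% and 28% figures measure data loss under random misses; they do not measure bias.

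**Conclusion.** The point holds for the thickness test and its Scheffe comparisons, on condition that at least one follow-up scan is missing. It rests on the standard form of the named method and on the documents' silence about missing scans. Its size depends on a miss rate the documents do not give; under the assumed 5% to 15% per visit, the test would lose between about one and a half and four of 10 subjects on average. The loss of precision is certain once a subject is removed. Distortion is only a possibility, and the simulated shifts illustrate an assumed mechanism rather than predict this study's result. The change is worth making because it is cheap; the point does not invalidate the study.

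**What to change.** In Section 5, replace the repeated-measures ANOVA with a linear mixed model: visit as a categorical factor, subject as a random effect, REML estimation with a small-sample degrees-of-freedom correction. State that it uses every available MRI from every enrolled subject, including scans obtained before withdrawal. Keep the Scheffe contrasts. Report the number scanned at each visit with the reason for each missing scan, so that the Section 4.3.1 means can be read against the model.

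At an assumed 10% miss rate the model would use about 10 + 27 = 37 scans from about 10 subjects, against 4 × 7.29 = 29.2 scans from 7.3 subjects. With no scan missing and a positive estimate of between-subject variance, the random-intercept model reproduces the planned F-test, so essentially nothing is given up.

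The cost is a short change to the SAP text and no new data. The downside is that the model assumes scans are missing at random given the observed thickness values. Bias can remain if subjects leave for reasons that their earlier thickness does not show. This is still a weaker assumption than the completers-only analysis generally needs.

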1 INTRODUCTION & RATIONALE

Chronic insertional Achilles tendinopathy is a common ailment in the general population. It is traditionally described as a phenomenon of overuse in both athletic and nonathletic individuals. Non-operative management usually consists of activity and shoe modifications, nonsteriodal anti-inflammatory medications (NSAIDs), and some form of physical therapy, which can be successful. In patients in whom conservative interventions fail, operative intervention is the next step. This intervention intails open detachment and debridement of the diseased Achilles tendon, calcaneal osteotomy, and reattachment of the Achilles. Often the diseased Achilles debridement leaves the tendon compromised in terms of its integrity and the remaining tendon will need augementation with a tendon transfer using the flexor hallucis longus (FHL).

The Rotation Medical Bioinductive Implant is a bioabsorbable device that provides a layer of collagen over injured tendons. This device is indicated for the management and protection of tendon injuries in which there has been no substantial loss of tendon tissue and can be implanted during a the standard open treatment for insertional Achilles tendinopathy. The device was first evaluated in a preclinical study of 23 sheep that was approved by the Colorado State University Institutional Animal Care and Use Committee. The device did not elicit an inflammatory response or a foreign body reaction. Histological analysis confirmed the device was completely absorbed after six months with integration of the new tendinous tissue to the underlying host tendon and a fibrocartilagenous transition zone at the tendon-to-bone insertion site. Tendon thickness at the implant site increased by approximately 2.5 millimeters due to induction of new tendinous tissue and remained stable one year after surgery.

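### The tendon-thickness test names no sphericity correction and relies on Scheffé; with a pooled error it could be insensitive to a moderate 1-to-2-year change, and paired-difference intervals would avoid this at almost no cost

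*Combined protocol and SAP*

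**What the plan says.** Section 5 covers this outcome in one sentence. "Changes in tendon thickness over the time of the follow up visits" are to be "assessed by a Repeated Measures ONEWAY ANOVA with a post hoc Scheffe". It does not mention sphericity, a correction, the error term for the post hoc comparisons, or whether baseline is one of the time levels.

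Section 4.3.1 makes thickness the first primary outcome, measured by MRI before surgery and at each follow-up. It adds a descriptive summary: the mean and SD of the "change in post-operative Achilles tendon thickness will be calculated at each follow-up interval". Section 7.7 sets the visits at "3 months, 1 year, and 2 years after discharge from the study procedure". Section 4.1 limits the study: "Up to 10 subjects will be enrolled and treated". Section 5 also states: "This is an initial feasibility study and not powered to address the hypotheses".

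No alpha, SD, between-visit correlation or expected late change is given for thickness.

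**The concern.** A one-way repeated-measures ANOVA without correction assumes sphericity, meaning that the difference between any two visits has the same variance. On the default reading, Scheffé then uses that one pooled error for every comparison.

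The design makes equal variances unlikely. Between baseline and 3 months the tendon is detached, debrided, re-attached and covered with the implant, and the flexor hallucis longus tendon may be added at the surgeon's discretion (Section 7.5). Those changes should differ a good deal between subjects. Section 2.1 expects the implant to be absorbed within 6 to 12 months and the tendon staples within about 12. The 1- and 2-year scans are therefore two looks at much the same healed tendon and should agree closely.

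A pooled error would then lend the variability of the surgical change to the late comparison. Section 4 describes the aim as long-term outcomes, and the 1-to-2-year change is the one comparison that lies wholly around or after expected absorption. Separately, Scheffé protects every conceivable contrast when only a handful are of interest, so it is wider than needed even where the pooled error is right.

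**Working it through.** The plan has no figure to reproduce. The inputs are:

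- From the documents: n = 10 at most; MRI at baseline, 3 months, 1 year and 2 years.
- Assumed: complete data, two-sided alpha 0.05, and k = 4 levels (baseline included) or k = 3 (follow-up visits only), because Section 5 allows either.
- Assumed moderate non-sphericity, in arbitrary thickness units: SDs 1.0, 1.5, 1.3, 1.3; correlations 0.4 with baseline, 0.6 between 3 months and each later visit, 0.9 between 1 and 2 years. Epsilon is 0.77 for k = 4.

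**Multipliers.** Scheffé = √[(k−1)·F₀.₉₅(k−1, (n−1)(k−1))].
- k = 4: √(3 × 2.96) = 2.98. k = 3: √(2 × 3.55) = 2.67.
- Unadjusted paired t on 9 df: 2.26. Strictest Holm step over four contrasts (alpha 0.0125): 3.11.
- Dunnett for three changes from baseline on 27 df: 2.49, so Scheffé is 2.98/2.49 = 1.20 times as wide for those three.

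**Pooled error.** Expected MSE = (trace of the covariance matrix − sum of all its elements/k)/(k−1).
- k = 4: (6.63 − 17.632/4)/3 = 0.741, so the implied SD of any difference is √(2 × 0.741) = 1.217.
- k = 3: (5.63 − 13.352/3)/2 = 0.590, implied SD 1.086.
- True SD of the 1-to-2-year difference: √(1.69 + 1.69 − 2 × 0.9 × 1.69) = 0.581.
- Overstatement: 1.217/0.581 = 2.09 (k = 4); 1.086/0.581 = 1.87 (k = 3).
- True SD of the baseline-to-3-month difference: √(1 + 2.25 − 2 × 0.4 × 1.5) = 1.432. The pooled value is 0.85 of this.

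**Late-contrast half-widths, k = 4.** Pooled Scheffé: 2.98 × 1.217/√10 = 1.15. Own-SD paired t: 2.26 × 0.581/√10 = 0.42. A loss of 1 SD of the difference (0.581) is about half the Scheffé half-width, which is why it is rarely detected.

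**Simulation, 100,000 trials of n = 10.** The F test's type I error is 6.6 to 6.9% for k = 4 and 7.1 to 7.3% for k = 3. Detection of a 1-to-2-year loss:

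| Loss, in SDs of the difference | Scheffé, k = 4 | Scheffé, k = 3 | Paired t, alpha 0.0125 | Paired t, alpha 0.05 |
|---|---|---|---|---|
| 1 | 1.4% | 11% | 55% | 80% |
| 2 | 55% | 84 to 85% | over 99% | over 99% |
| 1, sphericity true | 58% | 69% | 55% | 80% |

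**Sensitivity at 1 SD.** Three other assumed non-spherical structures give Scheffé detection of 0.1 to 3.5% (k = 4) and 2 to 26% (k = 3). Milder non-sphericity (epsilon 0.86) gives 18% for k = 4.

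**Coverage of the planned intervals, k = 4.** Scheffé covers about 98% for baseline to 3 months, 99% for baseline to each later visit, and about 96% for all six pairs jointly.

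**The case against.** The strongest reply is that every variance input is assumed. The documents do not say that Scheffé will use a pooled error, only that it will be used. Under sphericity Scheffé does slightly better at 1 SD than the strictest Holm step (58% against 55%), and the 80% comparator is unadjusted. The study is declared unpowered, and Section 4.3.1 reports mean changes anyway, so a fall in thickness could show descriptively. All of this stands, and it limits the point to a conditional one. It does not remove the case for an interval that is valid with or without sphericity: a study of at most 10 subjects mainly yields estimates, and Section 4.3.1 promises no interval and does not clearly cover the 1-to-2-year change.

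Two stronger readings are tempting and are not supported.

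- A reader might infer that the intervals for pre- to post-surgery change are too narrow, because the pooled standard error for baseline to 3 months is too small. An unadjusted pooled-t interval there would cover about 90%, but the plan does not use one. The planned Scheffé interval covers about 98%.
- A reader might infer that a late loss would almost always be missed and then called stable. Detection depends on the size of the loss, the late correlation and the number of levels. A loss of one between-subject SD of thickness (1.3 units here) would be found in 75% of trials with four levels and 94% with three. No section says that a non-significant late change will be read as stability; the statement in Section 1 that thickness "remained stable one year after surgery" concerns sheep.

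**Conclusion.** The point holds as a cheap improvement to the analysis. Section 5 names no safeguard against unequal variances of the visit differences, and the design makes them likely. If the post hoc error is pooled and the late scans correlate strongly, the overall test is mildly liberal (about 7% for a nominal 5%). The 1-to-2-year standard error is then roughly doubled, and a late loss of about 1 SD of the difference is largely invisible to Scheffé (about 1% or 11% detection). The insensitivity shrinks quickly for larger losses and disappears under sphericity. The comparisons with baseline err towards caution. These sizes rest on assumed SDs, correlations and alpha, with 10 complete subjects; the direction rests on the surgical timing and absorption period that the protocol itself describes.

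**What to change.** Replace the thickness sentence in Section 5 with:

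> For each follow-up visit versus baseline, and for the 1-to-2-year change, the mean paired difference is reported with a 95% confidence interval from that contrast's own differences (t, n−1 df). Any p-values are Holm-adjusted over these four contrasts.

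Delete Scheffé. If the overall ANOVA is kept, state which visits are its levels and use Greenhouse-Geisser degrees of freedom.

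This changes wording only and needs no new data. The price is 9 error degrees of freedom per contrast instead of 27 (four levels, 10 complete subjects), with little or no gain in power for the late contrast if sphericity does hold.
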